4.5.1 Datasets Analyzed

Efficacy summaries will be produced as described in Section 4.2. Efficacy summaries will be repeated for the Efficacy Evaluable Analysis Set as supportive evidence and to assess the robustness of efficacy findings. Efficacy summaries may also be repeated for the Intent-to-Treat Analysis Set if meaningfully different than the Modified Intent-to-Treat Analysis Set. A data listing of patients excluded from the Intent-to-Treat, Modified Intent-to-Treat, and Efficacy Evaluable Analysis Sets, to include the reason for exclusion, will be presented.

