# 3.1.1. Screening Period

At screening, the patient will provide a signed informed consent form prior to any study-related activities. Collection and shipment of a formalin-fixed paraffin-embedded (FFPE) tumor sample to the central pathology lab should occur as early as possible, and no later than 8 weeks following Cycle 1 Day 1 (see Section 4.1.1). The tumor sample will be used for central confirmation of EBV status and verification of lymphoma subtype. Additional screening evaluations must be performed within 28 days or 14 days before treatment start as defined in the Schedule of Events (Section 6.1). At the time of screening, patients should be advised around their options to store germ cells.

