## 9.3. Definition of Analysis Populations

The following 4 populations will be used in the analysis:

- 1. **Intent-to-Treat (ITT) population:** All patients who are enrolled into the trial, regardless of whether they received study treatment or not.
  - The ITT population will be used for the primary efficacy analysis. Patients will be analyzed according to their disease/cohort. If a patient has no post-baseline tumor assessment for efficacy, they will be counted as a treatment failure in this population analysis.
- 2. **Modified ITT (mITT) population:** All enrolled patients who have received at least one dose of study medication, met all eligibility criteria, and have at least one post-baseline tumor assessment for efficacy.
  - The efficacy analysis will also be performed on the mITT population as supportive evidence and/or sensitivity analyses. Patients will be analyzed according to their cohort and overall.
- 3. **Safety population:** All patients who have received at least one dose of study medication will be summarized for safety based on cohort and overall.
- 4. **PK population:** All patients with PK assessments.

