## 9.6. Efficacy Analysis

All efficacy analyses will be performed on the ITT population. Key efficacy analyses will be performed on the mITT population as supportive evidence and to assess robustness of efficacy findings.

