4.2 Analysis Sets

The analysis sets are defined as follows:

- Intent-to-Treat Analysis Set: All patients who are enrolled into the trial, regardless of whether they received study treatment or not.
- Modified Intent-to-Treat Analysis Set: All enrolled patients who have received
 at least one dose of study medication with a confirmed diagnosis of lymphoma
 subtype by central pathology review. The primary efficacy analysis will be
 performed in the Modified Intent-to-Treat Analysis Set per FDA guidance and
 historical precedent.
- Efficacy-Evaluable Analysis Set: All enrolled patients who have received at least one dose of study medication, met all eligibility criteria, and have at least one adequate (radiographic) post-baseline tumor assessment.
- Safety Analysis Set: Patients who have received at least one dose of study medication will be summarized for safety by cohort and over all patients combined.

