4.5.6.6 Use of an "Efficacy Subset" of Patients

The primary efficacy analysis will be performed in the Modified Intent-to-Treat Analysis Set; the Intent-to-Treat and Efficacy Evaluable Analysis Sets will be utilized as sensitivity analyses.

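### The SAP replaces the protocol's ITT primary set with a centrally confirmed mITT set, contradicts itself on whether ITT efficacy will be reported, and has no rule for missing central pathology

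*SAP*

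**What the plan says.** **Protocol.** Section 9.3 states that "The ITT population will be used for the primary efficacy analysis" and, for that set, "If a patient has no post-baseline tumor assessment for efficacy, they will be counted as a treatment failure". Section 9.6 repeats the choice: "All efficacy analyses will be performed on the ITT population". The protocol's mITT set is supportive only, and its definition (dosed, eligible, at least one post-baseline assessment) is close to what the SAP calls Efficacy-Evaluable.

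**SAP, primary set.** Section 4.2 redefines mITT as enrolled patients with "at least one dose of study medication with a confirmed diagnosis of lymphoma" subtype by central pathology review. It makes this set primary, giving FDA guidance and historical precedent as the reason. Section 4.8 declares the departure from the protocol.

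**SAP, reporting of ITT.** Section 4.5.1 says "Efficacy summaries may also be repeated for the Intent-to-Treat Analysis Set if meaningfully different" from mITT, and 4.8 keeps the same option. Section 4.5.6.6 says "the Intent-to-Treat and Efficacy Evaluable Analysis Sets will be utilized as sensitivity analyses", with no condition. Section 4.5.6.8, on the second-line subgroup, names only the mITT and Efficacy-Evaluable sets.

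**Central pathology.** Under Protocol Table 5, footnote d, eligibility rests on local pathology and central confirmation is not needed to start treatment. Protocol 3.1.1 has tissue shipped as early as possible and "no later than 8 weeks following Cycle 1 Day 1". Protocol 7.1.6 keeps patients with a discordant central result in the study. Neither document says how a missing, late or inadequate specimen affects mITT membership, or that central pathology review is masked to response.

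**The concern.** There are two separate weaknesses.

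The first is the reporting rule. The SAP's Introduction says the plan exists to avoid post hoc decisions and that it supersedes the protocol's analysis plan. Yet whether the protocol's own primary analysis appears at all depends, in 4.5.1 and 4.8, on a comparison that can be made only after both results are known, against a criterion that is nowhere defined. Section 4.5.6.6 points the other way, and nothing says which text governs.

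The second is the denominator. A requirement for confirmation treats two different groups alike: patients whom central pathology finds to have another subtype, and patients for whom it could reach no answer. The second group is still being formed after treatment starts, in an open-label trial, up to about the time of the first response scan at week 8. If patients who do badly early are more likely to end without a usable central result, the mITT ORR is raised.

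What is at stake is the headline ORR and its lower limit. These are what the SAP sets against reference rates at the interim and final analyses, and the interim result may support a declaration of overwhelming efficacy and an accelerated submission.

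**Working it through.** **Inputs.** The interim threshold is at least 26 responses in 40 second-line patients, ORR 65%, 95% CI 48% to 79%, said to exclude about 47% (SAP 4.5.6.3). SAP Table 4 sets this case against a 45% control rate, and 21/40 against 35%. SAP 4.4 indicates that the second-line mITT subgroup is used for the primary interim analysis, so the 40 are taken here as mITT patients. The number *k* of ITT patients outside mITT is not given; I assume about 5% to 20% of ITT.

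**Formula.** Clopper-Pearson 95% limits for *x* responders in *n*: lower = Beta quantile at 0.025 with parameters (*x*, *n* − *x* + 1); upper = Beta quantile at 0.975 with parameters (*x* + 1, *n* − *x*).

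**Reproducing the plan.**
- 26/40 = 65.0%, limits 48.3% and 79.4%. The SAP gives 48% and 79%.
- 21/40 = 52.5%, limits 36.1% and 68.5%. The SAP gives 36% and 68%.

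Both agree with the SAP.

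**From mITT to ITT.** If *k* ITT patients lie outside mITT and *r* of them responded, the ITT result is (26 + *r*)/(40 + *k*). The two extremes are *r* = 0 and *r* = *k*.

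| *k* | Share of ITT | All excluded are non-responders | All excluded are responders |
|---|---|---|---|
| 0 | 0% | 26/40 = 65.0% (48.3, 79.4) | same |
| 2 | 2/42 = 4.8% | 26/42 = 61.9% (45.6, 76.4) | 28/42 = 66.7% (50.5, 80.4) |
| 4 | 4/44 = 9.1% | 26/44 = 59.1% (43.2, 73.7) | 30/44 = 68.2% (52.4, 81.4) |
| 7 | 7/47 = 14.9% | 26/47 = 55.3% (40.1, 69.8) | 33/47 = 70.2% (55.1, 82.7) |
| 10 | 10/50 = 20.0% | 26/50 = 52.0% (37.4, 66.3) | 36/50 = 72.0% (57.5, 83.8) |

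With two excluded non-responders the lower limit is 45.6%, below the 47% the SAP says is excluded but still above Table 4's 45%. With four it is 43.2%, below 45% as well. In Table 4's middle row, two excluded non-responders turn 21/40 (lower limit 36.1%) into 21/42 = 50.0% (34.2%), which no longer excludes 35%.

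If the excluded patients respond at the same rate as the rest, the point estimate does not move.

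**The case against.** The case for the SAP is substantial. The change of set is declared in 4.8 with a reason in 4.2, and the SAP is to be final before any formal interim or final analysis. Patients excluded from each set are listed with reasons (4.5.1), each set is counted (4.3.1), and data are listed for all enrolled patients (4.1.1), so a reader could rebuild the ITT ORR. The conditional wording also calls for ITT when the sets differ, which is when it matters most. All of this stands. But the criterion is undefined, the verb is permissive, and listings do not replace a pre-specified estimate with its interval.

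Four stronger readings are tempting, and the documents do not support them.

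- *ITT will be shown only if it differs.* Section 4.5.6.6 plans it without condition. The finding is a contradiction, not a plan to withhold ITT.
- *mITT removes early failures.* It does not require a scan, and 4.5.6.2 counts non-evaluable patients as non-responders. The tissue pre-dates treatment, its availability is an entry requirement (Protocol 4.1.1, criteria 2a and 13) and must be confirmed at screening (Table 5, footnote d). Outcome-related loss is possible, not a stated rule. Still, 4.5.6.2 cannot restore a patient who never entered mITT.
- *The Simon error rates no longer hold.* SAP 4.7 words the gates on patients accrued and on the initial 21, and nothing applies mITT to them. The gates are response counts (2, 5 and 7), so removing non-responders leaves them unchanged.
- *The final result against 25% would flip.* 40/120 has a lower limit of 24.99% and 40/114 has 26.4%, but that is a knife-edge count. At 41/120 the limit is already 25.8%. SAP 4.7 itself treats 33.3% of 120 as excluding 25%, and SAP 4.5 places the primary expansion analyses in the second-line subgroup, about 50 to 60 patients.

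**Conclusion.** The concern holds as a defect of pre-specification. The primary set has moved from ITT to a centrally confirmed mITT. Sections 4.5.1 and 4.8 make ITT reporting optional and results-dependent, and 4.5.6.6 contradicts them. No rule covers patients whose central pathology is missing or inadequate.

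The size and direction of any bias cannot be derived from the documents. The illustration assumes that every excluded patient is a non-responder, and on that assumption two to four patients around the interim threshold take the lower limit from 48.3% to between 45.6% and 43.2%. The opposite assumption raises it. These are bounds, not a forecast. They show that so few patients can move the limit across the SAP's own reference rates, which is why the rule should be settled before results are seen. This should be changed, but it does not invalidate the design.

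**What to change.** 1. Report the IRC-assessed ITT ORR with its 95% Clopper-Pearson interval beside the mITT result, unconditionally, at the interim and final analyses, including for the second-line subgroup.
2. In SAP 4.5.1 and 4.8, delete the permissive verb and the condition about a meaningful difference, so that both agree with 4.5.6.6. Add ITT to 4.5.6.8.
3. In SAP 4.2, exclude from mITT, among treated patients, only those whom central pathology positively reclassifies. Keep patients with missing, late or inadequate tissue in the denominator. Stating that central pathology review is masked to response would close the remaining gap.

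The cost is SAP wording and one more set of tables. The reported ORR may be slightly lower.

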4.5.2 Measurements of Treatment Compliance

Compliance with both nanatinostat and valganciclovir will be determined as the total number of tablets taken divided by the expected number of tablets dispensed, multiplied by 100.

The total number of tablets taken will be determined as the number of tablets dispensed minus the total number of tablets returned. The expected number of tablets received will be determined as the number of tablets dispensed.

Dosing compliance will be summarized using descriptive statistics, for each cohort based on the Safety Analysis Set. The number and percentages of patients who are <80% compliant and $\geq80\%$ compliant within each cohort will be summarized. Treatment compliance will also be included in a by-patient data listing.

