# 5.2.2. Valganciclovir Administration

The daily dose of valganciclovir for patients ≥17 years of age is 900 mg orally (continuous treatment) in combination with nanatinostat. Patients with a CrCl 50-59 mL/min at study entry will receive valganciclovir 450 mg orally once daily as per Table 4. Patients will continue to receive nanatinostat plus valganciclovir in 28-day cycles until discontinuation as described in Section 7.2.3.

The daily dose of valganciclovir for patients ≤16 years of age is based on body surface area (BSA) and CrCl derived from a modified Schwartz formula, and is calculated using the equation below:

Adolescent dose (mg) =  $7 \times BSA \times Schwartz$  Creatinine Clearance

$$Mosteller\ BSA\ (m^2) = \sqrt{\frac{Height\ (cm)\ x\ Weight\ (kg)}{3600}}$$
 
$$Schwartz\ Creatinine\ Clearance\ (mL\ /\ min\ /\ 1.73m^2)\ = \frac{k\ x\ Height\ (cm)}{Serum\ Creatinine\ (mg\ /dL)}$$

Note: k value is 0.55 (boys <13 years and girls <16 years) or 0.7 (boys aged 13 to 16 years).

Patients should be monitored for serum creatinine levels regularly, consider changes in height and body weight, and adapt the valganciclovir dose as appropriate. Valganciclovir tablet dose is

determined based on the calculated valganciclovir dose in mg and available tablet strength (450 mg)  $\pm 10\%$  range of the tablet strength. For example, if the calculated dose exceeds 900 mg, a maximum dose of 900 mg should be administered. If the calculated dose is between 900 mg and 810 mg, a 900 mg dose (two 450 mg tablets) should be taken. If the calculated dose is between 809 mg and 405 mg, 450 mg dose (one 450 mg tablet) should be taken.

Adequate hydration should be maintained for all patients. For patients who develop an elevated creatinine while on study, their dose of valganciclovir should be adjusted (see Section 5.4.1).

In patients who are unable to tolerate oral dosing of valganciclovir, the Investigator will have the option of administering ganciclovir intravenously (IV) at 5 mg/kg QD. In patients who are receiving a dose of valganciclovir less than 900 mg orally once daily, the dose of ganciclovir will be reduced accordingly using the ratio of 900 mg valganciclovir to 5 mg/kg ganciclovir.

Valganciclovir absorption is affected by food. Therefore, patients should be instructed to take both valganciclovir and nanatinostat with food and not fasting.

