All dosages of study treatment prescribed and dispensed to the patient, and all dose adjustments during the study must be accurately recorded in the eCRFs.

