# 5.4. Dose Modifications of Nanatinostat and Valganciclovir

For patients who do not tolerate the protocol-specified dosing schedule, or develop toxicities, dose adjustments are permitted to allow the patient to continue study treatment. Dose adjustments, except for valganciclovir adjustments based on renal function (Section 5.4.1) must be approved by the Medical Monitor or Sponsor prior to implementing. These changes must be accurately recorded in the eCRFs.

Given the expectation that both study drugs are required for activity, both agents will be held and restarted in parallel. Requirements for dose modifications and criteria for resumption of dosing are presented in Table 3.

**Table 3:** Dose Modification Guidelines for Study Treatment-Related Toxicity

NCI CTCAE v5.0 Toxicity Grade	Action to be Taken with Study Drugs
Grade 4 neutropenia (ANC $< 0.5 \times 10^9/L$ )	
 
Interrupt nanatinostat/valganciclovir dosing.
 
Resume nanatinostat/valganciclovir at the same doses when ANC ≥1.0 × 10^9/L.
 

NCI CTCAE v5.0	
Toxicity Grade	Action to be Taken with Study Drugs
	
 
If the grade 4 neutropenia lasts more than 7 days or recurs, then reduce valganciclovir to 450 mg orally daily. If the reduced dose is tolerated for ≥4 weeks, then the valganciclovir dose may be increased to 900 mg daily.
 
Use of growth factors (G-CSF, GM-CSF) is permitted as per the ASCO
 

	2015 clinical practice guidelines (Smith 2015).
Grade 3 neutropenia (ANC $0.5 - <1.0 \times 10^9/L$ )	
 
If persistent (>7 days) then interrupt nanatinostat/valganciclovir dosing. Resume nanatinostat/valganciclovir at the same doses when ANC ≥1.0 × 10^9/L. If recurs and persists >7 days, then consider reducing valganciclovir to 450 mg orally daily.
 
Use of growth factors (G-CSF, GM-CSF) is permitted as per the ASCO 2015 clinical practice guidelines (Smith 2015).
 

Grade 4 thrombocytopenia (Platelet count <25 × 10  /L)	Interrupt nanatinostat/valganciclovir dosing.  Interrupt nanatinostat/valganciclovir dosing.
(Platelet count <25 × 10  /L)	• If thrombocytopenia resolves to ≤Grade 2 (>50 × 10  /L), then restart both drugs.
	• If recurs, then consider reducing valganciclovir to 450 mg orally daily.
Grade 3 anemia	Interrupt nanatinostat/valganciclovir dosing.
(Hemoglobin <8.0 g/dL)	• If anemia resolves to ≤Grade 2 (≥8.0 g/dL), then restart both drugs.

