	nanatinostat/valganciclovir at the same dose.

Abbreviations: ANC = absolute neutrophil count; CTCAE = Common Terminology Criteria for Adverse Events; G-CSF = granulocyte colony-stimulating factor; GM-CSF = granulocyte macrophage-colony stimulating factor; NCI = National Cancer Institute; PO = orally; QD = once daily.

Patients should be monitored approximately twice weekly for resolution of the toxicity. During a dose interruption, study days and procedures will continue to accrue until the end of the current cycle (see Schedule of Events in Section 6.1). If the dose interruption extends beyond the end of the cycle, the subsequent cycle will not begin until dosing has resumed. If the dose is held for more than 14 days, the Investigator should consult with the Medical Monitor before dosing resumes.

If a patient has multiple dose interruptions for study drug toxicity or has had to interrupt for more than 14 days, a dose reduction should be considered. Re-escalation of study drug dose may only be performed after approval by Medical Monitor.

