## 5.4.1. Dose Modifications for Patients with Renal Impairment

Patients ≥17 years of age who develop an elevated creatinine while on study should have their creatinine clearance (CrCl) recalculated and dose of valganciclovir adjusted per Table 4.

An estimated CrCl in adults is calculated from serum creatinine by the following formulas:

For serum creatinine measured in mg/dL:

For males = 
$$(140 - age [years]) \times (body weight [kg]) = XX mL/min$$
  
(72) × (serum creatinine [mg/dL])

For females = 
$$(140 - age [years]) \times (body weight [kg]) = XX mL/min \times 0.85$$
  
(72) × (serum creatinine [mg/dL])

For serum creatinine measured in µmol/L:

For males = 
$$(140 - age [years]) \times (body weight [kg]) \times 1.23 = XX mL/min$$
  
Serum creatinine (µmol/L)

For females = 
$$(140 - age [years]) \times (body weight [kg]) \times 1.23 = XX \text{ mL/min} \times 0.85$$
  
Serum creatinine (µmol/L)

For patients already receiving a dose of valganciclovir lower than that recommended in Table 4, the Investigator should discuss the amount of dose reduction with the Medical Monitor.

Table 4: Valganciclovir Dosing for Patients with Renal Impairment

Creatinine Clearance (mL/minute)	Valganciclovir Dose
≥60	900 mg once daily
40–59	450 mg once daily
25–39	450 mg every 2 days
10–24	450 mg twice weekly
<10 (on hemodialysis)	Not recommended (discuss with Medical Monitor)

Source: Valcyte USPI 2021(Genentech 2021) and SmPC 2018 (Roche 2018)

Note: Patients  $\geq$ 17 years of age receiving hemodialysis (CrCl less than 10 mL/min) cannot use valganciclovir tablets because the daily dose of valganciclovir tablets required for these patients is less than 450 mg. In this case the Investigator will have the option of administering ganciclovir IV at 5 mg/kg QD, after discussion with the Study Medical Monitor.

Patients 12 to 16 years of age who develop an elevated creatinine while on study should have their CrCl recalculated (by a modified Schwartz formula per Section 5.2.2) and dose of valganciclovir adjusted based on body surface area (BSA).

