## 5.7.3. Study Drug Compliance and Accountability

## **5.7.3.1.** Study Drug Compliance

Patient compliance with study drugs will be assessed by the Investigator and/or study personnel at each patient visit, and information provided by the patient and/or caregiver will be captured in the eCRF. This information must be captured in the source document at each patient visit. Paper diaries will be utilized to record doses and collect tablet counts.

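### The SAP's compliance ratio compares tablets dispensed with themselves, so a fully adherent patient can be scored below 80%

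*SAP*

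**What the plan says.** SAP 4.5.2 defines compliance, for each drug, as tablets taken over an expected number of tablets, times 100. It then defines both parts. The numerator: "The total number of tablets taken will be determined as the number of tablets dispensed minus the total number of tablets returned". The denominator: "The expected number of tablets received will be determined as the number of tablets dispensed". Results are summarised by cohort on the Safety Analysis Set, split at 80%, and listed by patient.

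The protocol provides for several situations in which tablets dispensed and tablets prescribed differ:

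- **Holds.** Under Protocol 5.4, for toxicity, "both agents will be held and restarted in parallel".
- **Valganciclovir reductions.** Protocol Table 3 includes reductions to 450 mg daily. Table 4 includes non-daily schedules such as "450 mg every 2 days".
- **Replacement of tablets.** Under Protocol 5.2.2, for patients who cannot tolerate oral valganciclovir, "the Investigator will have the option of administering ganciclovir intravenously (IV) at 5 mg/kg QD".
- **Stopping treatment**, which can fall partway through a supply (Protocol 3.1.2 and 7.2.3).

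The protocol also requires the data that a comparison with the prescribed dose would need. Section 5.2.2 requires eCRF recording of "All dosages of study treatment prescribed and dispensed to the patient", together with all dose adjustments. Section 7.2.4 requires the date of stopping. Section 5.7.3.1 provides for paper diaries and states that "information provided by the patient and/or caregiver will be captured in the eCRF".

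**The concern.** A compliance ratio should compare what a patient took with what the patient was told to take. Here the expected number is simply the dispensed number, so the prescribed dose, the schedule, holds, reductions and the stop date play no part. The ratio describes the share of dispensed tablets that did not come back.

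Two separate problems follow. First, the denominator lowers the score of adherent patients whose prescribed dose was less than the supply they were given. Second, the numerator treats every unreturned tablet as swallowed and cannot exceed the dispensed count, so it hides missed doses when tablets are not returned and cannot show intake above the prescribed dose. Changing the denominator does not cure the second problem.

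At stake is how the by-cohort table, its 80% split and the listing are read. A reader would take a patient below 80% as non-adherent, when the patient may only have followed a protocol-directed hold or stopped at progression.

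**Working it through.** **Inputs.** Nanatinostat: 10 mg tablets, 20 mg on 4 days per week (Protocol 5.1.1, 5.1.3), so 2 tablets × 16 dosing days = 32 per 28-day cycle. Valganciclovir: 450 mg tablets, 900 mg daily (Protocol 5.2, 5.2.2), so 2 × 28 = 56 per cycle. Quantities dispensed are not stated (Table 5 lists only a dispensing/return item), so supply is an assumption below.

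**Identity.** With D dispensed and R returned, compliance = 100 × (D − R)/D = 100 × (1 − R/D). It is below 80% exactly when R/D > 0.20.

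All patients in A to C are fully adherent; unused tablets are assumed returned and not carried forward.

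**A. Exact 28-day supply.** A directed 7-day hold inside a cycle returns 8 nanatinostat and 14 valganciclovir tablets. Both drugs give the same score:

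| Cycles | Nanatinostat | Valganciclovir | Score |
|---|---|---|---|
| 1 | 24/32 | 42/56 | 75.0% |
| 2 | 56/64 | 98/112 | 87.5% |
| 3 | 88/96 | 154/168 | 91.7% |
| 6 | 184/192 | 322/336 | 95.8% |

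Stopping at the middle of cycle c scores (c − 0.5)/c: 50.0%, 75.0%, 83.3% and 91.7% for c = 1, 2, 3 and 6. Valganciclovir reduced to 450 mg daily from Day 15 of the first cycle scores (28 + 14)/56 = 75.0% for that cycle.

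**B. Surplus supply s, no hold.** The score is 1/(1 + s): 90.9%, 83.3%, 80.0%, 76.9% and 66.7% for assumed surpluses of 10, 20, 25, 30 and 50%. It falls below 80% once the surplus exceeds 1/0.8 − 1 = 25%.

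**C. Assumed supply that just covers a visit 3 days late** (the window in Protocol 7.2.1). For 31 days this is 2 × 19 = 38 nanatinostat and 2 × 31 = 62 valganciclovir tablets. Visits on time and no hold: 32/38 = 84.2% and 56/62 = 90.3%. Adding one 7-day hold:

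| Cycles | Nanatinostat | Valganciclovir |
|---|---|---|
| 1 | 24/38 = 63.2% | 42/62 = 67.7% |
| 2 | 56/76 = 73.7% | 98/124 = 79.0% |
| 3 | 88/114 = 77.2% | 154/186 = 82.8% |
| 6 | 184/228 = 80.7% | 322/372 = 86.6% |

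**What reduces the effect.** With full carry-forward, a hold followed by resumed dosing gives R = 0 and a score of 100%. Hold days past the end of a cycle need not create returns, because "If the dose interruption extends beyond the end of the cycle, the subsequent cycle will not begin until dosing has resumed". Under scenario A, a 14-day hold starting on Day 22 scores 24/32 = 42/56 = 75.0% over one cycle; the same hold entirely inside the cycle scores 16/32 = 28/56 = 50.0%.

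**Opposite error.** A patient who takes 28 of 56 valganciclovir tablets and returns none scores (56 − 0)/56 = 100%.

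**With tablets prescribed as denominator**, the 7-day hold over one cycle scores 24/24 = 42/42 = 100%. The patient who took half and returned none still scores 100% unless recorded doses replace dispensed minus returned.

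**The case against.** The algebra is not in dispute; the case against concerns how much it matters.

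The ratio does equal adherence when the dispensed count matches the prescribed count and every untaken tablet is returned. Every percentage above rests on assumed dispensing practice, with supply details left to a Pharmacy Manual that is not part of these documents. The lowest scores come from short treatment: under scenario A a single 7-day hold stays above 80% from the second cycle on, and a stop at the end of a supply scores 100%. All of this stands. It limits what can be said about frequency but leaves the formula unchanged.

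Protocol 5.7.3.2 requires accounting for all supplied drug, and Protocol 8.1 and 8.8 require overdoses to be recorded. These safeguards may limit unreturned supply and document excess intake elsewhere, but neither enters the SAP ratio.

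Exposure (SAP 4.6.1), interruptions and reductions (4.6.2, 4.6.3) and disposition (4.3.1) are reported separately. They give context without correcting the ratio; the exposure summary gives duration and total mg with no comparison to the prescribed dose.

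Finally, netting out directed holds is a convention, and the documents do not say outright that hold start and stop dates, or every diary dose, are entered in the eCRF. That is fair. It is why the fix states the convention openly and gives the numerator a fallback.

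**Conclusion.** The definition is wrong as written. It names an expected number and then sets it equal to the dispensed number, and nothing else in the SAP corrects this. The SAP states in its Introduction that it supersedes the protocol's analysis plan, and the protocol offers no competing formula, so the ratio would be programmed literally.

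That a fully adherent patient can fall below 80% is shown from the protocol's own tablet strengths, schedule and hold rules, given an exact one-cycle supply, return of unused tablets and no carry-forward. How often this would happen cannot be computed. The events are plausible: in the earlier combination study (Protocol 1.2.4), 13 of 64 patients had Grade 3/4 anaemia and 13 had adverse events leading to drug withdrawal. That study mixed dose levels, so these counts show relevance and are not a misclassification rate.

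The consequence is minor. Compliance is descriptive, defines no analysis set in SAP 4.2 and feeds no efficacy endpoint.

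**What to change.** In SAP 4.5.2:

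1. **Denominator.** Replace it with tablets prescribed, separately for each drug. Sum from first dose to the recorded stop date using the dose and schedule in force in the eCRF, including non-daily valganciclovir schedules. Exclude directed holds and intravenous ganciclovir periods, count reductions at the reduced dose, and write this convention into the text.
2. **Numerator.** Use doses recorded in the diary or dosing eCRF where available; otherwise use dispensed minus returned.
3. **Missing information.** If a dispensed supply has neither a return count nor a dosing record, show the patient as not determinable in the table and flag the patient in the listing. Do not place such a patient in the group at or above 80%.

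The cost is a short text edit and somewhat more programming. Prescribed dosages, dose adjustments and the stop date are already required in the eCRF, compliance information is captured at visits, and a dosing eCRF exists (Protocol 8.1). Before finalising, confirm that hold dates and individual diary doses are captured; where diary doses are not, the fallback applies. No dose or clinical rule changes.
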